6.0 ADVERSE EVENTS

6.1 DEFINITIONS

Adverse Event (AE): any untoward medical occurrence in a patient or clinical study subject.

Serious Adverse Event (SAE): any untoward and unexpected medical occurrence or effect that:

- **Results in death**
- **Is life-threatening** – *refers to an event in which the subject was at risk of death at the time of the event; it does not refer to an event which hypothetically might have caused death if it were more severe*
- **Requires hospitalisation, or prolongation of existing inpatients' hospitalisation**
- **Results in persistent or significant disability or incapacity**
- **Is a congenital anomaly or birth defect**

Medical judgement should be exercised in deciding whether an AE is serious in other situations. Important AEs that are not immediately life-threatening or do not result in death or hospitalisation but may jeopardise the subject or may require intervention to prevent one of the other outcomes listed in the definition above, should also be considered serious.

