6.2 REPORTING PROCEDURES

All adverse events should be reported. Depending on the nature of the event the reporting procedures below should be followed. Any questions concerning adverse event reporting should be directed to the Chief Investigator in the first instance.

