6.3 Non serious AEs

All such events, whether expected or not, should be recorded

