6.4 Serious AEs

An SAE form should be completed and emailed to the Chief Investigator within 24 hours. However, relapse and death due to COVID -19, and hospitalisations for elective treatment of a pre-existing condition do not need reporting as SAEs.

All SAEs should be reported to the London Riverside REC where in the opinion of the Chief Investigator, the event was:

- 'related', ie resulted from the administration of any of the research procedures; and
- 'unexpected', ie an event that is not listed in the protocol as an expected occurrence

Reports of related and unexpected SAEs should be submitted within 15 days of the Chief Investigator becoming aware of the event, using the NRES SAE form for non-IMP studies. The Chief Investigator must also notify the Sponsor of all related and unexpected SAEs.

Local investigators should report any SAEs as required by their Local Research Ethics Committee, Sponsor and/or Research & Development Office.

Contact details for reporting [contact]**CI email (and contact details below)****Fax: N/A, attention [name]****Please send SAE forms to: [contact]****[contact] (Mon to Fri 09.00 – 17.00)****7.0 STATISTICS AND DATA ANALYSIS**

The prevalence of MDT-confirmed PC-ILD at both early (up to 6 months) and again at late (10-15 month) time-points and will be assessed within the total study population. The prevalence of broader radiological abnormalities and phenotypic patterns will also be assessed in a descriptive analysis, together with demographics, haematological and biochemical profiles, physiological performance, and patient-reported outcome measures. Analyses will be performed overall and stratified according to hospitalised and non-hospitalised, as well as severity of infection in hospitalised patients defined above.

Baseline and longitudinal changes in biomarkers reflecting PC-ILD evolution, including circulating factors and cell-types from detailed serological and cellular analysis, will be assessed in multilevel models for repeated measures to test associations according to the presence or absence of PC-ILD at late time points (10-15 months), and according to progression, resolution, or persistence of radiological patterns over follow up time points.

Analyses will be performed using standard epidemiological and statistical genetics methodology. This will include cross-sectional and longitudinal studies, and analyses of disease prevalence and incidence.

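### The SAE definition in 6.1 includes expectedness, which 6.4 leaves to the Chief Investigator, so a serious event that a site considers expected has no defined reporting route

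*Combined protocol and SAP*

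**What the plan says.** Section 6.1 gives two definitions. An adverse event (AE) is "any untoward medical occurrence in a patient or clinical study subject", with no condition on expectedness. An SAE is "any untoward and unexpected medical occurrence or effect that" meets a seriousness criterion such as death, threat to life or hospitalisation. The closing paragraph of 6.1 adds a judgement clause, "Medical judgement should be exercised in deciding whether an AE is serious in other situations", which does not mention expectedness.

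Section 6.2 says "All adverse events should be reported" and then "Depending on the nature of the event the reporting procedures below should be followed". It names no recipient and no deadline, though questions go to the Chief Investigator. Two procedures follow:

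- **6.3, non-serious AEs:** "All such events, whether expected or not, should be recorded".
- **6.4, SAEs:** a form goes to the Chief Investigator within 24 hours. COVID-19 relapse or death, and elective admissions for a pre-existing condition, are exempt. Then: "All SAEs should be reported to the London Riverside REC where in the opinion of the Chief Investigator, the event was" both related to a research procedure and unexpected, the latter meaning "ie an event that is not listed in the protocol as an expected occurrence". Such reports are due within 15 days, and the Sponsor must also be notified.

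**The concern.** Expectedness enters at two points. In 6.1 it helps decide whether an event is an SAE at all, and so whether a form is sent. In 6.4 it helps decide whether an SAE already reported to the Chief Investigator goes on to the REC. The first point has no stated standard and no stated judge. The second has both.

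If a site applies its own idea of what is expected at the first point, the Chief Investigator may never make the second judgement. At stake is oversight of serious events caused by the study's own procedures, which for Tier 2 visits (3.2.1) include blood sampling, lung function testing and an optional walk test. Practice could also differ between sites. Reporting by local investigators to their own committees, Sponsor or R&D office is tied to the same term in 6.4 and inherits the same condition.

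**Working it through.** No arithmetic applies. The check follows each kind of event through 6.1 to 6.4.

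1. **Serious, and unexpected in the site's view.** It meets the 6.1 definition. The form goes within 24 hours, the Chief Investigator judges relatedness and expectedness, and the REC is told if both are met. This route works.
2. **Not serious.** Section 6.3 applies, and the event is recorded whether or not it was expected. This route works.
3. **Serious, but expected in the site's view.** It fails the 6.1 definition, so 6.4 does not require a form. It is not non-serious, so 6.3 does not apply. Only the general sentence in 6.2 remains. Minor expected events are thus captured explicitly while serious expected ones are not.

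Next, compare the two tests of expectedness.

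| | 6.1 | 6.4 |
|---|---|---|
| Who judges | not stated | Chief Investigator |
| Against what | not stated | events the protocol lists as expected |
| When | before a form is sent | after the form arrives |
| Consequence | whether the event is an SAE | whether an SAE goes to the REC |

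Apart from the exemptions in 6.4, the protocol contains no list of expected events. Under the 6.4 test, a serious event related to a research procedure, and not exempt, therefore counts as unexpected and is reportable.

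A hypothetical case shows the gap. A Tier 2 participant faints after the research blood sample and is admitted. A site that regards fainting as a known effect of blood sampling, and the resulting admission as part of it, could read 6.1 as requiring no form. If the Chief Investigator judged the event related, 6.4 would make it reportable, because fainting is not on any list in the protocol.

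Finally, check which section departs from the rest. The separate expectedness test in 6.4 would be redundant if every SAE were already unexpected. The exemption for elective admissions, which are foreseeable by nature, would be largely unnecessary too. The judgement clause in 6.1 carries no expectedness condition. The rest of the safety section thus reads as though SAEs include expected events, and the two words in 6.1 are out of line with it.

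**The case against.** The strongest reply is that the documents do not show any event being lost. Four parts of it deserve an answer.

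- **Section 6.1 does not say that the site judges expectedness by its own lights.** The only definition in the protocol is in 6.4. Read that meaning into 6.1 and, since no list exists, no procedure-related serious event is screened out. This stands: loss occurs only where a site's view differs from the 6.4 test. But nothing in 6.1 points the reader to 6.4 for the meaning.
- **Section 6.2 requires all AEs to be reported, and the AE definition has no expectedness condition.** This also stands, as a partial safeguard. An event in the third group should still be reported in some form. Without a recipient or deadline, however, 6.2 does not replace the 24-hour route.
- **The named exemptions in 6.4 imply that other serious events are to be reported.** That is a fair reading of the intent. It supports bringing 6.1 into line more than it supports leaving it.
- **The study is observational, so the practical effect is small.** Agreed.

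A reader might go further and infer that sites do screen out serious events, or that no event a site thinks expected ever reaches the Chief Investigator. The documents support neither. The first would be a statement about conduct, and the text shows only what its wording allows. The second overlooks 6.2.

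**Conclusion.** The point holds as a contradiction in the reporting rules. Sections 6.1 and 6.4 disagree on where expectedness is judged, and a serious event that a site considers expected has no defined procedure. A related event that 6.4 would make reportable to the REC may therefore not reach the Chief Investigator by the SAE route.

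The conclusion rests on two assumptions: that a site may apply its own view of what is expected, which 6.1 neither requires nor prevents, and that this view may differ from the 6.4 test. If every site used the 6.4 definition, no procedure-related event would be missed.

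The documents give no event rate, so no count can be put on this. With blood sampling, lung function, an optional walk test and questionnaires at two obligatory visits and one optional visit, few research-related serious events are likely. The primary endpoint and its analysis are unaffected. The case for acting is that the gap lies in safety oversight and is very cheap to close.

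**What to change.** In the SAE definition in 6.1, delete the words *and unexpected*. Seriousness alone then triggers the 24-hour form. Relatedness and expectedness stay with the Chief Investigator under 6.4, and the existing exemptions there remain unchanged.

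Cross-referring 6.1 to the 6.4 definition would be weaker: it would leave the 6.4 test redundant and keep an expectedness judgement ahead of the form.

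Do not add a sentence limiting the forms to certain participants in order to save work. Sections 6.1 to 6.4 make no exclusion for data-only participants or those co-enrolled in PHOSP-COVID, and introducing one would narrow reporting in an edit meant to close a gap.

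The cost is a two-word amendment and some additional SAE forms for the Chief Investigator to review. The documents do not allow that number to be estimated.

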6.2 REPORTING PROCEDURES

All adverse events should be reported. Depending on the nature of the event the reporting procedures below should be followed. Any questions concerning adverse event reporting should be directed to the Chief Investigator in the first instance.

6.3 Non serious AEs

All such events, whether expected or not, should be recorded

6.4 Serious AEs

An SAE form should be completed and emailed to the Chief Investigator within 24 hours. However, relapse and death due to COVID -19, and hospitalisations for elective treatment of a pre-existing condition do not need reporting as SAEs.

All SAEs should be reported to the London Riverside REC where in the opinion of the Chief Investigator, the event was:

- 'related', ie resulted from the administration of any of the research procedures; and
- 'unexpected', ie an event that is not listed in the protocol as an expected occurrence

Reports of related and unexpected SAEs should be submitted within 15 days of the Chief Investigator becoming aware of the event, using the NRES SAE form for non-IMP studies. The Chief Investigator must also notify the Sponsor of all related and unexpected SAEs.

Local investigators should report any SAEs as required by their Local Research Ethics Committee, Sponsor and/or Research & Development Office.

Contact details for reporting [contact]**CI email (and contact details below)****Fax: N/A, attention [name]****Please send SAE forms to: [contact]****[contact] (Mon to Fri 09.00 – 17.00)****7.0 STATISTICS AND DATA ANALYSIS**

The prevalence of MDT-confirmed PC-ILD at both early (up to 6 months) and again at late (10-15 month) time-points and will be assessed within the total study population. The prevalence of broader radiological abnormalities and phenotypic patterns will also be assessed in a descriptive analysis, together with demographics, haematological and biochemical profiles, physiological performance, and patient-reported outcome measures. Analyses will be performed overall and stratified according to hospitalised and non-hospitalised, as well as severity of infection in hospitalised patients defined above.

Baseline and longitudinal changes in biomarkers reflecting PC-ILD evolution, including circulating factors and cell-types from detailed serological and cellular analysis, will be assessed in multilevel models for repeated measures to test associations according to the presence or absence of PC-ILD at late time points (10-15 months), and according to progression, resolution, or persistence of radiological patterns over follow up time points.

Analyses will be performed using standard epidemiological and statistical genetics methodology. This will include cross-sectional and longitudinal studies, and analyses of disease prevalence and incidence.

Analysis design and choice of controls will be dependent upon the precise nature of the research question. Identification of risk factors for a specific COVID-19 sequela would involve controls both from within UKILD-Long COVID (without the sequela) and serology-positive controls with prospective questionnaire and healthcare record linkage from Longitudinal Population Studies (for example, UK Biobank, Coronagenes, EXCEED) and pre-existing disease cohorts. Analyses aiming to characterise and understand the clinical features, subtypes and trajectories of sequelae (for example, sarcopaenia) would evaluate the cross-sectional and longitudinal clinical data and biomarkers of UKILD-Long COVID participants who are presenting with the sequelae being studied.

The participant organisations making up the UKILD-long COVID study group have extensive experience of development of, and collaborative use of, disease-specific and general population cohort studies both nationally and internationally enabling access to control populations and alignment of research strategies for rapid validation and replication of findings.

Statistical significance thresholds will be defined in advance of each analysis and will take into account issues of multiple testing and *a priori* evidence.

Data and all appropriate documentation will be stored for a minimum of 10 years after the completion of the study, including the follow-up period.

Project statistician: [name] email:

[contact]
National Heart and Lung Institute
[name]
[name]

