The PHOSP COVID study (ISRCTN10980107) is a national consortium that provides a platform to study the long-term consequences of COVID-19 hospitalisations [18]. An expected 10,000 individuals hospitalised by COVID-19 are to be included in baseline assessments after testing positive on PCR for SARS-CoV-2 and will be recruited through the PHOSP platform. The study described here will aim to recruit a further 2000 individuals, with proven COVID-19, who were not hospitalised but presented to Long-COVID clinics with persistent respiratory symptoms such as breathlessness or cough and are referred for cross-sectional imaging (computer tomography, CT) at baseline (3 months weeks after their first COVID-19 symptoms) [19]. A total of up to 12,000 people will be assessed for longitudinal follow up into the UKILD-Post COVID study. Following assessment of Post COVID patients at baseline (~3-6 months post infection as defined above), those with clinical and radiological features suggestive of ILD will be included into the UKILD-Post COVID study population. Where there are contraindications for CT and if clinically indicated, participants will be eligible for a research-guided 3D ultrashort echo time (UTE) proton MRI as a surrogate for CT. Where individuals meet criteria for initial study inclusion (COVID-19 and clinical indication for CT scanning) but have no clinical, radiological or physiological features of ILD they will be invited to enroll as part of the control cohort for follow up.

This protocol details the research partnership between Imperial (BREATHE Respiratory hub partner), and partner organizations.

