3 STUDY DESIGN

Prospective observational study of hospitalised and non-hospitalised patients post- infection with SARS-CoV-2. The study aims to recruit 2000 individuals, with proven COVID-19, who were not hospitalised but presented to Long-COVID clinics with persistent respiratory symptoms such as breathlessness or cough and are referred for cross-sectional imaging (computer tomography, CT) at baseline (3 months weeks after their first COVID-19 symptoms). The study will run for 18 months.

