4.2 Inclusion Criteria

Tier 1 criteria 'Data Only' participation

- 1) Age >18 years old -99 years old
- 2) Evidence of SARS-CoV-2 infection confirmed by PCR or serology at any point during the duration of the pandemic
- 3) Breathlessness and/or a clinical indication for a chest CT scan as per clinician judgment
- 4) Participants who have been identified and consented for tier 1 may not meet the inclusion criteria for tier 2 (below) but consent to researcher access to all clinical data relating to their health care during the pandemic and any subsequent follow up in relation to their COVID recovery.

Tier 2

- 1) Age >18 years old -99 years old
- 2) Evidence of SARS-CoV-2 infection confirmed by PCR or serology 3 months (+/- 6 weeks) earlier
- 3) Clinical indication for a chest CT scan as per clinician judgment
- 4) Participants who have been identified and consented for the main PHOS-PCOVID study are also eligible to join this study (if PHOSP-COVID is still open to recruit at that time).
- 5) Allow inclusion of patient who are receiving up to 10mg of prednisolone a day

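### The denominator of the primary prevalence is undefined: section 1.2 can be read as selecting it on ILD features, while sections 3 and 4.2 set no such condition

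*Combined protocol and SAP*

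**What the plan says.** The primary objective (2.1) is the prevalence of ILD 12 months after infection, and the primary comparison in 3.1 sets non-hospitalised against hospitalised patients. The only analysis statement for it is in 7.0: prevalence at early (up to 6 months) and late (10–15 month) "time-points and will be assessed within the total study population". Results are given overall and by hospitalisation and severity. No analysis set is named.

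The documents offer three candidates for that population.

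- **Everyone assessed.** Section 1.2: "A total of up to 12,000 people will be assessed for longitudinal follow up". This is an expected 10,000 hospitalised people from PHOSP-COVID plus 2,000 who were not hospitalised.
- **Everyone eligible.** Section 3 describes the 2,000 as people "who were not hospitalised but presented to Long-COVID clinics with persistent respiratory symptoms such as breathlessness or cough and are referred for cross-sectional imaging". In 4.2, Tier 1 asks for "Breathlessness and/or a clinical indication for a chest CT scan as per clinician judgment", and Tier 2 asks for a clinician-judged CT indication. Neither section mentions ILD features.
- **The population named in 1.2.** After baseline assessment, "those with clinical and radiological features suggestive of ILD will be included into the UKILD-Post COVID study population". Of people who "meet criteria for initial study inclusion (COVID-19 and clinical indication for CT scanning) but have no clinical, radiological or physiological features of ILD", it says "they will be invited to enroll as part of the control cohort for follow up". No number, ratio or sampling fraction is given for these controls.

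**The concern.** A prevalence means little until its denominator is fixed, and here the denominator of the headline result can be read in three ways. The reading that matters most is 1.2, the only text that says who enters the study population. Taken literally, it brings people in because they have features of the outcome and adds feature-free people only as far as they accept an invitation. The share with ILD among those enrolled would then partly reflect recruitment. Stratifying by hospitalisation does not remove this, because the selection operates inside each stratum.

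Three smaller gaps affect the same denominator:

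- Section 1.2 leaves people with some but not all features (for example, symptoms with a clear CT) in neither group.
- Tier 1 admits people on breathlessness alone, while the endpoint in 2.3 is radiological. The imaging appendix expects CT in each patient, but 4.2 does not require one for these entrants.
- Tier 1 accepts infection at any time in the pandemic, so some entrants may have no imaging in the early or late window.

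**Working it through.** The plan gives no sample size, target prevalence or precision, so there is no figure of its own to reproduce. The check asks what happens if 1.2 sets the denominator.

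**Inputs**

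- *p*, true ILD prevalence among those assessed: 24% (assumption). It borrows the upper figure in 1.1 for fibrotic change on the initial CT, which is not MDT-diagnosed ILD at 12 months. 10% is also shown (assumption).
- *s*, sensitivity and specificity of baseline features for ILD, taken as equal: 100%, 90% or 80% (assumption).
- *r*, uptake among feature-free people divided by uptake among people with features: not in the documents, so shown as a range. Within each feature class, uptake is assumed unrelated to ILD.

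**Crude prevalence among those enrolled**

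Crude = [p·s + p(1−s)·r] / {p·s + (1−p)(1−s) + [p(1−s) + (1−p)s]·r}

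Example with p = 0.24, s = 0.9, r = 0.5: the numerator is 0.216 + 0.012 = 0.228. The denominator is 0.216 + 0.076 + (0.024 + 0.684)(0.5) = 0.646. The ratio is 35.3%.

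| p | r | s = 100% | s = 90% | s = 80% |
|---|---|---|---|---|
| 24% | 1.25 | 20.2% | 20.9% | 21.6% |
| 24% | 1 | 24.0% | 24.0% | 24.0% |
| 24% | 0.8 | 28.3% | 27.4% | 26.5% |
| 24% | 0.5 | 38.7% | 35.3% | 32.1% |
| 10% | 0.5 | 18.2% | 16.1% | 14.3% |

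**Comparison between strata**

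Suppose the true prevalence is 24% in both strata, with r = 0.8 in one and 0.5 in the other. The crude figures then differ by 10.4, 7.9 or 5.6 points (s = 100%, 90%, 80%), although there is no real difference. A common r creates no gap between equal prevalences, but it still distorts a real contrast. With s = 100% and true values of 24% and 10%, the prevalence ratio is 2.40 at r = 1 and 38.7/18.2 = 2.13 at r = 0.5.

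**Does weighting recover the target?**

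Take 2,000 assessed (assumption), p = 24% and s = 90%. Then 584 have features and 1,416 do not. With uptake of 80% and 40% (r = 0.5), 467.2 and 566.4 enrol, of whom 345.6 and 19.2 have ILD. Crude: 364.8/1,033.6 = 35.3%. Weighted by the inverse enrolled fraction: (345.6/0.8 + 19.2/0.4)/2,000 = 480/2,000 = 24.0%.

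**Cost in precision**

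Var = p(1−p)/N + Σ W²·p_h(1−p_h)(1/n_h − 1/N_h), summed over the two feature classes. The class shares W are 0.292 and 0.708, and the class prevalences p_h are 0.740 and 0.034. The first term is 9.12×10⁻⁵ and the feature class adds 0.70×10⁻⁵. The feature-free class adds 0.29, 1.74 or 6.09×10⁻⁵ at r = 1, 0.5 or 0.2. The standard errors are 1.0, 1.1 and 1.3 percentage points.

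**The case against.** The strongest reply is that the plan has two stages: 4.2 governs entry, and 1.2 only sorts entrants into an ILD cohort and a control cohort. Much supports this. Section 1.2 itself names an initial study inclusion of COVID-19 plus a CT indication, which closely matches Tier 2. Section 4.1 requires participants to satisfy the inclusion and exclusion criteria, and 7.0 speaks of controls from within the study. Section 1.2 is also a rationale, while 4.2 is the operative eligibility section. On that reading the feature-selection bias does not arise. What stands is that the documents never state it and 7.0 does not say which stage is the denominator.

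A reader might go further in three ways that the documents do not support.

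- *The reported prevalence will be inflated.* This requires the 1.2 denominator and lower uptake among controls. No uptake is stated, and with r above 1 the error runs the other way.
- *The hospitalised comparison is biased.* PHOSP-COVID participants are screened under a separate protocol, so the uptake ratio could differ between strata, but nothing shows that it does.
- *Every reading limits the result to symptomatic or CT-referred people.* This fails for the 12,000 assessed, because 1.2 attaches no symptom or CT condition to the 10,000 hospitalised.

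**Conclusion.** The point holds and should be fixed. The primary prevalence has no defined denominator, and 1.2 on its plain wording conflicts with 3 and 4.2 about who is in it. If the 1.2 population is used, the crude figure depends on relative control uptake, and the hospitalised versus non-hospitalised comparison is biased if that ratio differs between strata. Equal uptake of people with and without features gives no bias.

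The size cannot be taken from the documents. The illustrative shift, from 24% to 32–39% at r = 0.5 or to 20–22% at r = 1.25, rests entirely on assumed values of p, s and r. Under the 4.2 or 1.2 readings, the estimate applies to symptomatic or CT-referred people, which is narrower than 2.1 says. Confidence is medium, because the two-stage reading may well be what the sponsor intends.

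**What to change.** 1. **Reconcile 1.2 with 3 and 4.2.** State that ILD features sort eligible people into the ILD and control cohorts and do not decide membership of the prevalence denominator.
2. **Define the denominator in 7.0.** Use people with confirmed infection and a clinical indication for chest CT who have imaging (CT, or the UTE MRI surrogate allowed in 1.2) in the early or late window being reported. Give the number without in-window imaging. Report separately Tier 1 participants who entered on breathlessness alone and have no imaging. Align 2.1 with this population.
3. **Record uptake.** Where available, keep aggregate assessed and enrolled counts by baseline feature class (ILD-suggestive, partial, none, unknown) and hospitalisation stratum. Beside the crude prevalence, report a sensitivity estimate weighted by the inverse enrolled fraction. Say that it does not correct for loss between enrolment and the late window. If the counts cannot be obtained, label the crude figure as prevalence among enrolled participants only.

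The cost is a few sentences in 1.2, 2.1 and 7.0, a small counting task for the direct care teams, a PHOSP-COVID extract and one extra estimate. Pre-screening is from notes, so feature class may be unknown for some people who never enrol, and the PHOSP-COVID counts may be incomplete. The weighted interval would be slightly wider: in the illustration the standard error rises from about 1.0 to 1.3 points as relative control uptake falls from 1 to 0.2. Steps 1 and 2 settle the definition by themselves; step 3 shows how far uptake could matter.
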